5.6.3.1.2 Individual participant changes of laboratory values

A shift table will be provided for the number and percentage of participants experiencing CTCAE grade 0, 1, 2, 3, or 4 values (as applicable) at Baseline to minimum/maximum post-Baseline CTCAE grade.

5.6.3.2 Vital signs

Vital signs, including body temperature, heart rate (or pulse rate), systolic blood pressure, and diastolic blood pressure will be assessed and analyzed.

5.6.3.2.1 Vital sign values over time

Descriptive statistics for the absolute value and change from Baseline for each vital sign parameter will be provided by weight-categorized dose group at each timepoint.

5.6.3.2.2 Individual participant changes of vital sign values

The number and percentage of participants experiencing at least 1 markedly abnormal value (Appendix 6.1.9.2) for a vital sign variable will be summarized by weight-categorized dose group for the Initial Treatment period, OLE Period, and the combined periods.

5.6.3.3 Columbia suicide severity rating scale (C-SSRS)

The C-SSRS is a standardized and validated instrument developed for the assessment of the severity and frequency of suicidal ideation and behavior. The C-SSRS defines 5 subtypes of suicidal ideation and behavior in addition to self-injurious behavior with no suicidal intent.

The incidence of study participants with suicidal ideation, suicidal behavior, suicidal ideation or behavior, and self-injurious behavior will be summarized by weight-categorized dose group through the Initial Treatment Period and through the Initial and OLE Treatment Periods combined. A listing of all C-SSRS questionnaire data will be provided. A listing of all participants who reported at least 1 suicidal ideation or behavior will also be provided.

5.6.3.4 PHQ-9

The PHQ-9 is a multipurpose instrument for screening, diagnosing, monitoring, and measuring the severity of depression. The PHQ-9 scores for depression range from 0 to 27, with higher scores indicating worse state. A score of 5 to 9 is considered to be minimal symptoms of depression. A score of 10 to 14 is considered to be minor depression, dysthymia, or mild major depression. A score of 15 to 19 is considered to indicate moderately severe major depression, and a score ≥ 20 is considered to be severe major depression. The PHQ-9 will be self-administered by the study participant and will be assessed by the study personnel at the scheduled visits.

The number and percentage of participants with scores below 5, between 5 and 9, between 10 and 14, between 15 and 19, and greater than 20 in PHQ-9 will be summarized as a shift from Baseline by visit and weight-categorized dose group based on observed values. Descriptive statistics for the PHQ-9 scores will be summarized by weight-categorized dose group and visit. A by-study participant listing of the PHQ-9 questionnaire data will be provided by weight-categorized dose group including the change of PHQ-9 scores from the previous visit. The PHQ-9 data source will be displayed in the listing.

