7.2 Participant discontinuation/withdrawal from the study

Participants are free to withdraw from the study at any time, without prejudice to their continued care.

A participant may withdraw from the study at any time at his/her own request, or may be withdrawn at any time at the discretion of the Investigator for safety, behavioral, compliance, or administrative reasons.

Investigators are expected to continually assess the balance of burden to each participant against the observed and anticipated clinical benefit, and to recommend study withdrawal if the benefit-risk balance is not favorable.

If the participant withdraws consent/assent for disclosure of future information, the Sponsor may retain and continue to use any data collected before such a withdrawal of consent/assent.

If a participant withdraws from the study, he/she may request destruction of any samples taken and not tested, and the Investigator must document this in the site study records.

See the Schedule of Activities ([Table 1-1](#) and [Table 1-2](#)) for data to be collected at the time of early discontinuation (Early Discontinuation Visit [EDV]) and follow up (SFU) and for any further evaluations that need to be completed.

Investigators should contact the Medical Monitor, whenever possible, to discuss the withdrawal of a participant in advance.

Participants must be withdrawn from the study if any of the following events occur:

1. Participants **must be referred** immediately to a mental healthcare practitioner (ie, licensed psychiatrist or clinical psychologist) for further assessment of any SIB and/or any evidence of major depression, if any of the following events occur:
 - Active suicidal ideation as indicated by a positive response (“Yes”) to Question 5 of the “Since Last Visit” version of the C-SSRS
 - Any suicidal behavior since last visit
 - Severe depression as indicated by a PHQ-9 score ≥ 20The mental health consultation will be documented in source documentation.
2. Participant or legal representative withdraws consent/assent to participate in the study.
3. There is confirmation of a pregnancy in a female study participant, as evidenced by a positive pregnancy test during the study. (For further information see [Section 8.3.5.](#))

4. The Sponsor or a regulatory agency requests withdrawal of the participant.
5. Participant has a diagnosis of active TB, an NTMB infection, or LTBI during the study. (For further information see Section 8.2.5.3.7.)

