5.6.3.1.1 Laboratory values over time

For tables where data are summarized by visit, unscheduled and repeat visits will not be summarized, but these data will be included in listings. Additionally for tables where data are summarized by visit, summaries of the Initial Treatment Period will not include the SFU visit since sample sizes will be small, but these data will be included in listings. For tables where multiple measurements over a period of time are considered (as in shift tables), unscheduled and repeat visits will be considered as long as they were collected in the period being summarized (values observed more than 140 days after the last administration of study medication are not considered). All summaries will be presented in International System of Units and will be based on observed case values. In the case where laboratory values are below the LLQ, then these will be set to the midpoint between 0 and the lower limit of quantification for the purpose of summarizing the data. The following summaries will be presented:

- A summary of the absolute and change from Baseline values in each laboratory variable by weight-categorized dose group and visit will be presented.
- A summary of the number and percentage of participants with a given CTCAE grade (0, 1, 2, 3, or 4) based on minimum/maximum post-baseline value by laboratory variable and weight-categorized dose group will be presented. The criteria used for CTCAE grade classification is provided in Section 6.1.9.1.
- A shift table of the number and percentage of participants experiencing CTCAE grade 0, 1, 2, 3, or 4 values (as applicable) at Baseline to maximum post-Baseline CTCAE grade will be presented, by laboratory variable and weight-categorized dose group.
- A summary of the number and percentage of participants experiencing treatment-emergent markedly abnormal (TEMA) values will be presented for each weight-categorized dose group for the Initial Treatment Period, OLE Period, and the combined periods. The TEMA laboratory values are defined similarly to TEAE as those lab values assessed on or following the first dose of study treatment through the final dose of treatment +20 weeks (140 days) with a severity of CTCAE Grade 3 and above.
- A by-participant listing of all laboratory data (including urinalysis) will be provided. This listing will be presented by weight-categorized dose group and will include center,

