participant identifier, age, sex, race, weight, visit, laboratory variable, result (with abnormal values flagged as “L” or “H” accordingly) and unit.

The table for markedly abnormal liver function tests (LFTs) will contain data beyond the CTCAE Grade 3 thresholds outlined in order to allow for a more thorough review of elevated LFTs. There will be one table, which will list the count and percentage of participants meeting the below criteria at any time during the study:

- AST (aspartate aminotransferase): >3xULN (upper limit of normal), >5xULN, >8xULN, >10xULN, >20xULN
- ALT (alanine aminotransferase): >3xULN, >5xULN, >8xULN, >10xULN, >20xULN
- AST or ALT: >3xULN, >5xULN, >8xULN, >10xULN, >20xULN
- Total Bilirubin: >1.5xULN, >2xULN
- ALP: >1.5xULN

For any participant with at least one markedly abnormal LFT (AST >3xULN, ALT >3xULN, bilirubin >3xULN, or ALP >1.5xULN) the New Ratio (nR) will be calculated as the ratio of either maximum ALT or maximum AST (whichever is higher) to ALP, all expressed as multiples of their ULN as follows:

- $nR = [\text{maximum}(\text{AST}/\text{ULN or AST}/\text{ULN})]/(\text{ALP}/\text{ULN})$

Potential drug induced liver injury (pDILI) will be summarized (all criteria must be met at the same assessment):

- (AST or ALT $\geq 3x\text{ULN}$) and Total Bilirubin $\geq 1.5x\text{ULN}$
- (AST or ALT $\geq 3x\text{ULN}$) and Total Bilirubin $\geq 2x\text{ULN}$

In addition, potential Hy's Law cases will be summarized with the LFT lab data. The following definition will be used:

- [AST $\geq 3x\text{ULN}$ or ALT $\geq 3x\text{ULN}$] and Total Bilirubin $\geq 2x\text{ULN}$ in the absence of ALP (Alkaline phosphatase) $\geq 2x\text{ULN}$

In order to meet the above potential Hy's Law laboratory criteria, a subject must experience the elevation in bilirubin and ALT or AST (and the absence of ALP elevation) at the same visit. For example, a subject who experiences a $\geq 2x$ ULN elevation of bilirubin at one visit and a $\geq 3x\text{ULN}$ elevation in ALT (or AST) at a subsequent visit has not fulfilled the Hy's law criteria. Follow-up information should be reported if an alternative etiology is identified during investigation and monitoring of the participant.

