6.1.4 Prior/concomitant/follow-up medications

Prior medications include any medications that started prior to the start date of study medication. Concomitant medications are medications taken at least one day in common with the study medication or with a start date greater than the last dose of study medication + 28 days. Any medication that started prior to the first dose of IMP and continued after will be classified as both prior and concomitant. Such medications will therefore be counted in the tabulations for both prior and concomitant medication.

The number and percentage of participants taking concomitant medications will be summarized by Anatomical Therapeutic Chemical (ATC) class for each dose group and overall, in the SS. Prior medications and prior antibiotic medications will be summarized similarly.

A by-study participant listing of all concomitant medications will be provided.

Concomitant medications will also be summarized for the Initial Treatment Period, OLE Period, and the combined periods. If participants have duplicate concomitant medication entries with the same date and time, the data will be listed with a flag to identify duplicates. Tables will count duplicates once, but listings will contain all occurrences.

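### Two safety-table rules misclassify values as written: a PHQ-9 score of exactly 20 falls in no shift-table band, and the two low-glucose limits in SAP Table 6-3 disagree

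*SAP*

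**What the plan says.** **PHQ-9.** SAP 5.6.3.4 gives the scale: "The PHQ-9 scores for depression range from 0 to 27". It then interprets the top of it: "a score ≥ 20 is considered to be severe major depression". The next paragraph tabulates shifts from Baseline for "scores below 5, between 5 and 9, between 10 and 14", then "between 15 and 19, and greater than 20 in PHQ-9". Protocol 9.4.1.7 has the same five bands. Protocol 8.2.4.2 defines the severe category as 20 or more, and Protocol 7.2 uses that threshold in its referral and withdrawal list ("Severe depression as indicated by a PHQ-9 score" of 20 or more).

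**Glucose.** SAP 6.1.9.1 defines markedly abnormal as CTCAE Grade 3 and above and says its tables give the Grade 3 cut points. In Table 6-3 the glucose row has a low limit of <40 mg/dL or <1.7 mmol/L and a high limit of >250 mg/dL or >13.9 mmol/L. SAP 5.6.3.1.1 fixes the reporting unit: "All summaries will be presented in International System of Units". It also refers to 6.1.9.1 for the grading criteria.

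**nR (minor).** SAP 5.6.3.1.1 says in words that nR is the higher of maximum ALT and maximum AST over ALP, each as a multiple of its ULN. The formula beneath it takes the maximum of AST/ULN and AST/ULN, so ALT does not appear.

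**The concern.** These rules feed the safety tables of an adolescent study in which safety is a secondary objective.

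Screening PHQ-9 scores of 15 or more are excluded (Protocol 5.2, criterion 31), so a score of 20 on study would normally be a deterioration from entry. A shift-from-Baseline table exists to show exactly that. Coded literally, it would have no cell for the lowest score that the documents call severe.

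For glucose, the count of participants with a treatment-emergent markedly abnormal low value depends on which column of Table 6-3 is programmed. The SI column, which the reporting rule makes operative, is the narrower of the two.

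**Working it through.** **1. PHQ-9 bands.** Inputs: integer scores from 0 to 27, and the five bands in SAP 5.6.3.4, taking "between" as inclusive.

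| Band | Scores covered | Number |
|---|---|---|
| below 5 | 0–4 | 5 |
| 5 to 9 | 5–9 | 5 |
| 10 to 14 | 10–14 | 5 |
| 15 to 19 | 15–19 | 5 |
| greater than 20 | 21–27 | 7 |

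The bands cover 5 + 5 + 5 + 5 + 7 = 27 of the 28 scores. The one left out is 20. With a last band of 20 or more, the count is 8 and all 28 scores are covered.

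**2. Glucose limits.** Inputs: the four glucose figures in Table 6-3.

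- Factor implied by the high pair: 250 / 13.9 = 17.99 mg/dL per mmol/L. Allowing for rounding of 13.9 (13.85 to 13.95), the range is 17.92 to 18.05.
- Factor implied by the low pair: 40 / 1.7 = 23.5. Allowing for rounding of 1.7 (1.65 to 1.75), the range is 22.9 to 24.2.
- The two ranges do not overlap, so rounding cannot explain the difference.
- Low limit converted with the high pair's factor: 40 / 17.99 = 2.22 mmol/L (2.22 to 2.23 over the rounding range).
- Stated SI limit converted back: 1.7 × 17.99 = 30.6 mg/dL.
- Relative difference: 1.7 / 2.22 − 1 = −23%.

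The factor from the molar mass of glucose (18.016, an assumption not stated in the documents) gives the same result: 40 / 18.016 = 2.22.

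**3. Control on the other dual-unit rows of Table 6-3.**

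- Calcium: 12.5 / 3.1 = 4.03 and 7.0 / 1.75 = 4.00. These agree within rounding.
- Magnesium: 3.0 / 1.23 = 2.44 and 0.9 / 0.4 = 2.25. With 0.4 given to one decimal (0.35 to 0.45), the second range is 2.00 to 2.57, which contains 2.44.

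Only the low-glucose pair is inconsistent beyond rounding.

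**4. Scale in a table.** The plan is for at least 20 participants per dose group, so one participant is at most 1/20 = 5 percentage points of a full dose group. The PHQ-9 shift and markedly abnormal tables are also split by weight-categorized dose, where one participant is a larger share. This is the size of one affected case, not an estimate of how many there will be.

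**5. nR.** With a = AST/ULN, b = ALT/ULN and c = ALP/ULN, the sentence gives max(a, b)/c and the formula gives a/c. They differ only when b > a, and the formula is then too low by the factor b/a.

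**The case against.** The strongest answer is that little is lost. A PHQ-9 score of 20 still enters the by-visit descriptive statistics and the participant listing, which shows change from the previous visit. All laboratory values are listed, and Protocol 8.2.3 requires clinically relevant laboratory changes to be recorded as adverse events. All analyses are descriptive (SAP section 2). This stands, and it limits the point to the summary tables.

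It can also be said that the governing rule for markedly abnormal values is CTCAE Grade 3 and above, version 4.03 (SAP 5.1.1.5 and 5.6.3.1.1), so a programmer could grade directly from that source. But the SAP refers to 6.1.9.1 for the criteria, and the table there gives two different limits.

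Four stronger readings are tempting but not supported:

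- **That severe depression would go unmanaged.** The Protocol 7.2 trigger is 20 or more and does not depend on the table bands.
- **That Grade 3 low glucose is certainly undercounted.** The documents show only that the two limits disagree. The undercount follows if 40 mg/dL is the intended limit, which they do not settle.
- **That the nR slip hides liver cases.** nR is computed only for participants already flagged with an abnormal liver test, and the pDILI and Hy's Law criteria do not use it. The sentence above the formula makes the intent plain.
- **That the concomitant-medication rule in SAP 6.1.4 has a reversed inequality.** That rule adds drugs "with a start date greater than the last dose of study medication + 28 days". However, it is joined by "or" to drugs sharing a day with study medication, and SAP 5.6.1.1 counts 28 days after the last dose as exposure. On that reading the first limb covers those 28 days and the second adds later drugs. Protocol 6.8 also records treatments in the follow-up period as concomitant. The wording is ambiguous, but an error is not shown.

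**Conclusion.** Both classification rules are wrong as written. Exactly one PHQ-9 score, 20, has no band in the shift table, in both documents. The two low-glucose limits differ by about 23%, so values from 1.7 to <2.2 mmol/L (about 31 to <40 mg/dL) are markedly abnormal by the conventional column and not by the SI column used for reporting.

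The PHQ-9 result assumes integer scores and inclusive bands. The glucose result rests on the row's own high pair and needs no outside grading text. It shows that the row contradicts itself, not which figure is right. The nR formula is a near-clerical error.

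The practical effect is small. No primary PK result, efficacy estimand or participant-management rule changes, and the documents give no basis for predicting how many participants would be affected. The corrections are still worth making, because a safety table should not omit the lowest severe score or give a count that depends on the unit column.

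**What to change.** - **SAP 5.6.3.4 and Protocol 9.4.1.7:** change the last PHQ-9 band from greater than 20 to 20 or more.
- **SAP Table 6-3:** check the low-glucose row against the Grade 3 limit in the CTCAE version the SAP names, and make the two columns agree. If 40 mg/dL is the intended limit, the SI entry is <2.2 mmol/L.
- **SAP 5.6.3.1.1 (minor):** write nR = max(ALT/ULN, AST/ULN) / (ALP/ULN).

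The cost is three short text corrections, one mirrored in the protocol, and a re-run of the PHQ-9 shift table, the outputs that use the low-glucose limit, and nR if it was coded from the formula. SAP version 3.0 gives database lock as part of its rationale, so the changes may need to be documented as a dated correction. They do not depend on the results.

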9.4.1.7 PHQ-9

The number and percentage of participants with scores below 5, between 5 and 9, between 10 and 14, between 15 and 19, and greater than 20 in PHQ-9 will be summarized as a shift from Baseline by visit and dose group based on observed values.

A by-study participant listing of the PHQ-9 questionnaire data will be provided by dose group.

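### The PHQ-9 shift table has no category for a score of exactly 20, the lowest score that both documents call severe

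*SAP*

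**What the plan says.** SAP 5.6.3.4 first describes the scale: "The PHQ-9 scores for depression range from 0 to 27, with higher scores indicating worse state". It then names the severity bands, ending with the statement that "a score ≥ 20 is considered to be severe major depression". The next paragraph of the same section sets the shift-table categories. They begin "The number and percentage of participants with scores below 5, between 5 and 9, between 10 and 14, between 15 and 19", and the top of the list reads "between 15 and 19, and greater than 20 in PHQ-9 will be summarized as a shift from Baseline by visit". The table is by visit and weight-categorized dose group, on observed values.

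Protocol 9.4.1.7 plans the same table with the same top cut-off: "between 15 and 19, and greater than 20 in PHQ-9 will be summarized as a shift from Baseline by visit and dose group". Protocol 8.2.4.2 defines the severe band as 20 or more, in agreement with the SAP's definition. Protocol 7.2 also uses 20 or more as its action threshold ("Severe depression as indicated by a PHQ-9 score", followed there by the value).

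No other section of either document assigns a score of 20 to a shift category. SAP Appendix 6.2, which lists the departures from the protocol's planned analyses, says nothing about PHQ-9.

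**The concern.** A categorical safety table should place every possible score in exactly one category. Here the score left out is the lower boundary of the most serious band. The severe row of the table would therefore not match the severity definition printed one paragraph above it.

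That boundary matters for how the table is read. Exclusion criterion 31 in Protocol 5.2 bars a PHQ-9 score of 15 or more, so enrolled participants should normally start at 14 or below. A later score of 20 would then be a move up of at least two bands, from 10-14 or lower past 15-19 into severe. A shift table exists to show moves of that kind.

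The gap also leaves the programmer with a choice that the plan does not settle: put 20 in the severe row, put it in 15-19, or leave it out. The plan fixes its categories in advance so that such choices are not made after the data are seen.

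**Working it through.** **Inputs**

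- Score range: 0 to 27 (SAP 5.6.3.4). I take scores as whole numbers. The documents do not say so outright, but bands such as 5-9 and 10-14 meet without a gap only on a whole-number scale. That gives 27 - 0 + 1 = 28 possible scores.
- Categories as written: <5, 5-9, 10-14, 15-19, >20 (SAP 5.6.3.4, Protocol 9.4.1.7).
- Severe band as defined: >=20 (SAP 5.6.3.4, Protocol 8.2.4.2, Protocol 7.2).

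**Coverage of the scale**

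| Category as written | Scores held | Count |
|---|---|---|
| <5 | 0-4 | 5 |
| 5-9 | 5-9 | 5 |
| 10-14 | 10-14 | 5 |
| 15-19 | 15-19 | 5 |
| >20 | 21-27 | 7 |
| Total | | 27 of 28 |

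The only score in no category is 20, and no score falls in two. If the top category is >=20 it holds 20-27, which is 8 scores. The total becomes 5 + 5 + 5 + 5 + 8 = 28, with no gap and no overlap. As written, then, the top row holds 7 of the 8 scores that the documents define as severe.

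**Size in the table**

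The documents give no PHQ-9 distribution, so the number of participants affected cannot be estimated. The effect of one participant with a score of 20 at a given visit can be shown:

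- Complete arm of exactly 20: 1/20 = 5.0 percentage points. If that participant stays in the denominator, the categories account for 19/20 = 95.0%.
- Weight-categorized groups: the documents do not give the split. Assuming 5 to 15 participants per group, one participant is between 1/15 = 6.7 and 1/5 = 20.0 percentage points.

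The planned arm size is at least 20, and denominators at later visits depend on who is still observed, so the 5-point figure is an illustration for one case only.

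Whether the percentages fall short of 100 depends on the denominator. SAP 5.1 bases safety summaries on observed data and shows the denominator in the table. A participant with an observed score of 20 would be in such a denominator but in no row. If the programmer drops the record from both, the percentages total 100 and the omission cannot be seen in the table.

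**The case against.** The strongest reply is that this is an evident slip of wording. The other four categories match the severity bands, and the fifth lacks only the words 'or equal to'. The correct band stands in the preceding paragraph, and a careful programmer would probably use it. PHQ-9 is not among the listed endpoints (SAP Table 1-1), and SAP Section 2 makes all analyses descriptive. No test, estimate or dose decision depends on this table.

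That stands as a limit on importance. It does not remove the error: the category list is the operative instruction for the table, and a silent correction would leave the output in disagreement with the plan.

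A reader might infer more than the documents support in three ways:

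- *That a severe case would be lost to safety review.* It would not. Under SAP 5.6.3.4 a score of 20 still enters the by-visit descriptive statistics and the by-participant listing, which also shows the change from the previous visit. Discontinuation reasons are tabulated (SAP 5.2), related adverse events enter the TEAE tables (SAP 5.6.2.2), and potential neuropsychiatric events go to adjudication (SAP 5.6.2.4.2). The Medical Monitor and the DMC also review neuropsychiatric events (Protocol 8.2.4).
- *That 20 is the severe score most likely to occur.* Neither document gives any basis for this.
- *That the missing score is plainly one requiring withdrawal.* In Protocol 7.2 the list heading reads "Participants must be withdrawn from the study if any of the following events occur", and Protocol 8.2.4.2 points to that section for withdrawal criteria. The item itself, however, requires only immediate referral to a mental healthcare practitioner. The two statements need reconciling, and I take no view on which should govern.

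**Conclusion.** The point holds as a definite but narrow error. As written in both documents, the shift-table categories omit one of 28 possible scores, and that score is the threshold for severe depression under the documents' own definition. Followed literally, a participant scoring 20 is left out of the severe row and the percentages may not total 100.

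The consequence is limited to one descriptive safety table. It arises only if a participant has a PHQ-9 score of exactly 20 at a tabulated visit. Most such scores would be post-Baseline, given the exclusion at 15 or more. Participant protection does not depend on this table. The conclusion rests on whole-number scoring and on a literal reading of the category list. The wording is most likely an oversight, since nothing in SAP Appendix 6.2 suggests an intended change of cut-off.

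**What to change.** In SAP 5.6.3.4, replace 'greater than 20' with '20 or greater' and program the top category as PHQ-9 >=20. Record the departure from Protocol 9.4.1.7 in SAP Appendix 6.2, or correct the protocol at its next amendment. A protocol amendment for this alone is not needed.

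SAP version 3.0 gives database lock as part of its rationale. If the table has already been produced, check how any score of 20 was classified and state the rule in a footnote.

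The cost is one phrase in the SAP, one line in the appendix and one condition in the program. No new data are needed.

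Separately, reconcile the heading of the mandatory list in Protocol 7.2 with the text of its first item, so that the consequence of meeting the PHQ-9 threshold is stated once and consistently.

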 - NOTE: The hepatitis C antibody test is a standard test used at screening to determine eligibility, and hepatitis C RNA testing is optional and only performed when the antibody test is positive in order to consider participants with positive hepatitis C antibody test for enrollment into the study. Where hepatitis C RNA testing is unavailable, a positive hepatitis C antibody test will be used for exclusion.

Other exclusions

27. Participant is part of the Investigator site personnel directly affiliated with this study and/or their immediate families. Immediate family is defined as a spouse, parent, child, or sibling, whether biological or legally adopted.
28. Criterion deleted
29. Participant has sensitivity to any of the study interventions, or components thereof, or drug or other allergy that, in the opinion of the Investigator or Medical Monitor, contraindicates participation in the study.
30. Presence of active suicidal ideation, or positive suicide behavior as evidenced by any of the following criteria:
- Participant has been diagnosed with suicidal behavior within the previous 6 months
 - Suicidal ideation in the past 6 months prior to the Screening Visit as indicated by a positive response ("Yes") to either Question 4 or Question 5 of the "Baseline/Screening" version of the C-SSRS.

- Participants with a lifetime history of suicidal ideation or behavior (more than 6 months prior to the Screening Visit) will be evaluated by a mental healthcare practitioner (ie, licensed psychiatrist or clinical psychologist) to determine whether they are eligible for participation.
31. Participant has been diagnosed with severe depression in the past 6 months, or has presence of moderately severe major depression or severe major depression as indicated by a score ≥ 15 using the Patient Health Questionnaire 9 (PHQ-9).
- Participants with a screening PHQ-9 score of 10 to 14, will be referred to a mental healthcare practitioner (ie, licensed psychiatrist or clinical psychologist) to determine whether they are eligible for participation.
32. History of psychiatric inpatient hospitalization within the past year before enrolling into the study.

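### The top PHQ-9 shift category starts above 20, so a score of exactly 20, which the SAP itself calls severe, has no category

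*SAP*

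**What the plan says.** SAP 5.6.3.4 first describes the instrument: "The PHQ-9 scores for depression range from 0 to 27, with higher scores indicating worse state". It then gives severity bands, the highest being that "a score ≥ 20 is considered to be severe major depression". The next paragraph defines the shift table. Its categories are below 5, 5 to 9, 10 to 14, and then "between 15 and 19, and greater than 20 in PHQ-9 will be summarized as a shift from Baseline by visit and weight-categorized dose group".

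Protocol 9.4.1.7 has the same top category: "and greater than 20 in PHQ-9 will be summarized as a shift from Baseline by visit and dose group". The other protocol text on the severe band includes 20. Section 8.2.4.2 defines severe major depression as 20 or more, and criterion 1 of section 7.2 lists "Severe depression as indicated by a PHQ-9 score" of 20 or more among the events that require immediate mental-health referral, under the heading of mandatory withdrawal.

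SAP Appendix 6.2, which records departures from the protocol's planned analyses, does not mention the PHQ-9 categories. SAP Amendment 1 (section 6.4.2, change 24) added descriptive statistics to the PHQ-9 section and did not touch the boundary.

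**The concern.** Two adjacent paragraphs of one SAP section disagree on where the severe band starts. The definition includes 20 and the table category does not. The category below stops at 19, so a score of 20 has nowhere to go.

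That score is the lowest in the severe range and the one at which the protocol's strictest PHQ-9 action begins. In protocol 7.2, criterion 11 covers scores of 15 to 19 (when they have risen by 3 points) and criterion 1 covers 20 and above, so the action bands meet without a gap. The table's bands do not. A table programmed literally could not be reconciled with the list of participants who met criterion 1 on PHQ-9, and its severe count could be too low.

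**Working it through.** **Inputs**

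- Score range: whole numbers 0 to 27, that is 28 possible scores (SAP 5.6.3.4).
- Severe band by definition: 20 to 27, that is 8 scores (SAP 5.6.3.4; protocol 8.2.4.2).
- Table categories: below 5; 5 to 9; 10 to 14; 15 to 19; above 20 (SAP 5.6.3.4; protocol 9.4.1.7).
- Planned group size: at least 20 per dose group (SAP 1.2 and 3).

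**Coverage as written.** Assign each score from 0 to 27 to a category and count:

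| Category | Scores | Count |
|---|---|---|
| below 5 | 0–4 | 5 |
| 5 to 9 | 5–9 | 5 |
| 10 to 14 | 10–14 | 5 |
| 15 to 19 | 15–19 | 5 |
| above 20 | 21–27 | 7 |

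The sum is 5 + 5 + 5 + 5 + 7 = 27 of 28. The one score without a category is 20. Within the severe range the table covers 7 of 8 scores.

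**Coverage with a top category of 20 or more.** The last count becomes 8, and 5 + 5 + 5 + 5 + 8 = 28. Every score falls in exactly one category, with no gap and no overlap.

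**Where it applies.** The shift is by visit. Reading the treatment-period columns of protocol Table 1-1 as Weeks 0, 1, 4, 8, 12, 16 and 20 (the sampling weeks in SAP 5.7.1.1), PHQ-9 is marked at 5 visits after Baseline. Table 1-2 has 10 marks, the first at Week 20, which adds 9. The same boundary is therefore used at 5 + 9 = 14 post-Baseline time points. Exclusion criterion 31 bars entry at scores of 15 or more, so the gap should matter for post-Baseline scores, not for the Baseline side of the shift.

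**Size per occurrence.** If one participant of *n* observed at a visit scores 20, the severe percentage is too low by 1/*n* and the categories sum to (*n* − 1)/*n*.

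- *n* = 20 (one dose group): shortfall 1/20 = 5 percentage points; categories sum to 19/20 = 95%.
- Weight-categorized group, assumed *n* = 10: 1/10 = 10 points. Over an assumed range of 5 to 15: 1/5 = 20 points down to 1/15 = 6.7 points.

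Neither document gives a PHQ-9 distribution, so the expected number of scores equal to 20 cannot be computed.

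**The case against.** The best reply is that this is a wording slip whose intended meaning is plain. The four lower categories fit the stated severity bands, the definition stands one paragraph above, and 20 or more is used wherever else the severe band is defined. A careful programmer would probably program it that way. The error is also easy to detect and loses no data. SAP 5.1 shows denominators as n/Nsub, so categories summing to 19 of 20 would be visible. The standard statistics include the maximum, and the by-participant listing carries every score. Referral under protocol 7.2 is a conduct rule that does not depend on this table, so no participant's safety is affected. Finally, a participant withdrawn after scoring 20 would normally contribute at about one visit, so the 14 time points are not 14 separate losses.

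Most of this stands, and it limits the weight of the point. It does not close the gap. No current text assigns 20 to a category, and the boundary is written out in words in both documents, so it is not a lost symbol. A table specification should not need the programmer to override it.

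**Conclusion.** The point holds and is minor. As written, the PHQ-9 shift table omits exactly one of 28 scores, and that score is the lower limit of the severe band.

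Each participant scoring 20 at a visit lowers the severe count by one: 5 percentage points with 20 observed in a dose group, and 10 points in an assumed weight-categorized group of 10 (20 to 6.7 points for 5 to 15). If nobody else at that visit scores 21 or more, the severe row shows a count of zero instead of one. The impact depends on two things: that the category is programmed literally, and that someone scores exactly 20, the frequency of which is unknown. PHQ-9 is not a listed endpoint, and neither the primary PK analysis nor the PS0021 dose choice depends on this category.

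**What to change.** In SAP 5.6.3.4, change the top shift category to 20 or more, so that it matches the severity definition in the same section and withdrawal criterion 1. Add a line to SAP Appendix 6.2 recording this as a correction to protocol 9.4.1.7. The cost is one boundary in a table already planned, with no new output, no new data and no change to study conduct.
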